Informal caregiving is demanding and stressful. This stress may exceed the caregiver's ability to adapt, and many eventually become care recipients themselves as years of stress and deferred self-care put them at increased risk for illness. Self-care refers to the behaviors undertaken to maintain health and manage illness. Engaging in self-care may improve health status, defined as physical functioning and mental well-being. Caregivers of adults with heart failure (HF) are an understudied group. HF is extremely common. Most HF patients remain in the community through the end of their lives, depending on informal caregivers to assist them. The trajectory of illness in HF is highly variable, which limits the use of palliative care and respite services. As a consequence, HF caregivers report significant stress and poor self-care. Health coaching, a support intervention, can improve self-care in patients, but studies evaluating HF caregivers are limited, as are studies of the cost-effectiveness of support interventions for caregivers. Even less is known about the effect of caregiver support interventions on HF patient outcomes. Caregiving duties often confine caregivers to the home and many are unable to attend in-person sessions, so we have developed and pilot tested a virtual support intervention (ViCCY ["Vicky"] - Virtual Caregiver Coach for You), that we propose to evaluate among HF caregivers. Using a randomized controlled trial (RCT) design, we will enroll informal HF caregivers with poor self-care (Health Self-Care Neglect scale score ≥2), randomizing them 1:1 to an intervention or control group. Both groups will receive standard care augmented with Health Information (HI) delivered through the Internet, but the ViCCY caregiver group will also receive 10 front-loaded coaching support sessions tailored to individual issues. The control group will have access to the same HI resources over the same interval, using the same Internet program, but without coaching support. At baseline and 3, 6, 9, and 12 months, we will collect self-reported data on self-care, stress, coping, and health status. At 6 months, we will compare ViCCY to HI alone to assess intervention efficacy using intent-to-treat analysis. Our pilot data suggest that addition of support provided by the health coach will make ViCCY more efficacious than HI alone. A sample of 250 caregivers (125/arm) will provide >90% power to detect significant differences between the groups on the primary outcome of self-care (Aim 1). We will collect quality adjusted life years (QALYs) and health care resource use in caregivers over 12 months to assess cost-effectiveness of ViCCY (Aim 2). To explore the effect of caregiver outcomes on HF patients' outcomes (hospitalization rates, hospital days, mortality rates, QALYs) over a 12-month period (Aim 3) and knowing that not all HF patients will participate, we will consent a subgroup of the HF patients cared for by these caregivers (at least 40 dyads). If shown to be efficacious and cost-effective, our virtual health coaching intervention can easily scaled to support millions of caregivers worldwide. This application addresses the NINR strategic plan and is directly responsive to PA-18-150.

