In preparation for this proposal, we conducted three pilot studies to adapt the intervention for caregivers. We first enrolled seven homebound female spouse caregivers of HF patients and interviewed them to identify stressors associated with caregiving. When we described the planned program, all were receptive to the electronic intervention and five of the seven women wanted to participate ("I need help desperately"). 71 In the second pilot study, we tested four methods of distance communication – telephone, tablet (iPad) with video, laptop computer with video and a detachable webcam, and touchscreen videophone. The iPad facilitated privacy by allowing the caregiver to move to a private place while conversing and was preferred over other devices ("the iPad is just less threatening"). In the third study, we assessed feasibility of our planned methods and pilot-tested the ViCCY intervention. 150 We enrolled four HF caregivers (white female spouses, mean age 66 ± 8.5 years) and gave each an iPad. Health coaches engaged each caregiver in 8 support sessions over a 3-month period. Each session lasted approximately 1 hour. Data were collected at enrollment and three months later using most of the methods proposed below. Table 1 shows change in the main target variables. Technology problems were more common in coaches than caregivers and were quickly resolved with assistance. Together these pilot studies illustrate that caregivers are interested in participating, they are comfortable with the tablet technology, and our proposed methods are feasible. We learned to hire coaches adept with technology and to ensure that participants have a strong Internet connection.

Table 1. Results from Pilot Study of Four Caregivers	Baseline Score (SD)	3-Month Follow-up Score (SD)
Perceived Stress Scale (lower is better)	20.7 (4.3)	18.2 (0.96)
Health Self-Care Neglect Scale (1-10 possible range, lower is better)	3.2 (2.5)	1.2 (1.2)
SF-12 Health Status, Mental Component Score (higher is better)	52.1 (9.1)	55.6 (4.3)

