- **C.6.** Intervention ViCCY. In addition to augmented standard care HI, caregivers randomized to ViCCY will receive 10 front-loaded sessions of virtual health coaching by trained RNs (Section C.6.a) over 6 months with content based on the theoretical framework and our prior research (**Table 3**, next page). As shown in **Figure**

**3**, sessions are weekly initially and decrease in frequency over time. ViCCY incorporates the factors essential in caregiver interventions; it is a psychosocial approach that is personalized and tailored to be flexible; is multidimensional, providing support for coping with perceived stress while fostering self-care; and is sufficient in dose, based on our pilot work. We refined our approach based on caregiver input to focus on *relieving* stress rather than intensifying demand and burden, thereby promoting caregivers' ability to respond to stressors

with adaptive coping. We aim to build motivation to gain the knowledge and skills needed to achieve self-identified health goals. 180 We focus on identifying personal values, solving problems, and transforming goals into action using a combination of psychological and behavioral interventions. 181

We use motivational interviewing in all ViCCY sessions. 182 Observations are presented to the caregiver in a way that

2 weekly 3 biweekly 2 triweekly 3 monthly sessions sessions sessions

**Figure 3**. Intervention sequence in Virtual Caregiver Coach for You (ViCCY) Treatment Arm. A total of 10 sessions are planned with booster sessions provided if requested by the caregiver. Between sessions, caregivers will complete "homework" (i.e. strategies to use and practice), which will be reviewed by the RN to monitor how these activities worked for the caregiver. At the end of the 6-month intervention period the RN will sever the virtual relationship, referring the caregiver to the HI website for further support.

builds confidence, motivates action, and enhances self-care by breaking the cycle of negative self-perception and emotions with the knowledge, skills, and beliefs needed to engage in healthy behaviors. We discuss goal-setting and action-planning in early sessions. Consistent with motivational interviewing, information (e.g., reasons for specific patient behavior) is given only if and when the caregiver is receptive to it.

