**C.14.2.** Aim 2: To estimate the cost and cost-effectiveness of ViCCY over 12 months. We hypothesize that caregivers randomized to ViCCY vs. HI only will have **H2a**: Higher QALYs measured with the SF-6D derived from the SF-36; and **H2b**: Lower health care resource use. The primary outcomes of this analysis include the difference in costs (intervention cost minus cost offsets), the difference in QALYs measured with the SF-6D, and the incremental cost effectiveness ratio (the difference in costs divided by the difference in QALYs). Costs will include both the costs of intervention implementation (number and length of intervention contacts, RN time to assess need for and delivery of the intervention, technology expenses, supervision time, and initial training). Cost offsets include the costs of health care (detailed below) and the difference in workplace productivity collected for both study groups. QALYs will be used to assess effectiveness. We hypothesize that compared to HI, ViCCY will require more resources for intervention implementation, but will reduce use of other health care resources. It is unclear if the changes in health care resource use or labor productivity will fully offset the intervention implementation costs (leading to a finding of dominance: lower cost and greater effect) or if net costs will be positive (leading to a finding of cost-effectiveness). We will follow a micro-costing approach in which all clinically relevant resources used in the study groups will be tracked and converted to costs using appropriate price weights.

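### The Aim 2 cost-effectiveness ratio credits caregivers' workplace productivity but names no charge for their time in coaching, so its numerator fits neither a payer nor a broader perspective

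*Combined protocol and SAP*

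**What the plan says.** Section C.14.2 takes the cost difference between arms as the cost of the intervention less offsets, and divides it by the difference in QALYs.

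- **Intervention cost.** The items listed are "number and length of intervention contacts, RN time to assess need for and delivery of the intervention, technology expenses, supervision time, and initial training".
- **Offsets.** "Cost offsets include the costs of health care (detailed below) and the difference in workplace productivity collected for both study groups".
- **Perspective.** Later in C.14.2, health care use is converted to payer costs with Medicare fees. The only resources expressly excluded are those of research and data collection.
- **What only ViCCY caregivers do.** The opening summary states that "the ViCCY caregiver group will also receive 10 front-loaded coaching support sessions tailored to individual issues", and C.6 gives the same number. Figure 3 adds homework: "Between sessions, caregivers will complete" strategies to practise. C.6 also provides between-session check-ins by the nurse and booster sessions on request.
- **How productivity is measured.** Table 5 lists a 7-day work performance questionnaire given at baseline and at 3, 6, 9 and 12 months. It also asks about hours of unpaid work, but C.14.2 takes only workplace productivity into the ratio.

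**The concern.** Workplace productivity is an item on the caregiver's side of the ledger. Once it is in the numerator, the ratio is no longer a payer ratio, and the caregiver's time input to the intervention belongs there too. No section lists or values that input, and the arms differ on it by design.

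If the ratio is instead meant to be a payer ratio, caregiver time is rightly absent, but then the productivity offset does not belong. As written, the numerator is consistent under neither reading.

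C.14.2 says it is not known whether offsets will exceed the implementation cost and so yield dominance. With a small QALY gain, an omitted cost of a few hundred dollars per caregiver can move the ICER by thousands of dollars per QALY. Cost-effectiveness is a named aim and part of the argument for scaling the programme up.

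**Working it through.** The plan states no ICER, unit cost, hourly value or QALY gain, so there is no figure to reproduce. Two things can be checked.

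**1. Would the productivity measure pick up session time anyway?**

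Figure 3 gives 2 weekly, 3 biweekly, 2 triweekly and 3 monthly sessions: 2 + 3 + 2 + 3 = 10. Laid end to end, with a month as 52/12 weeks, they fall at about weeks 1, 2, 4, 6, 8, 11, 14, 18.3, 22.7 and 27. This timeline is illustrative. The follow-up interviews fall at weeks 13, 26, 39 and 52.

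- On the nominal dates, the 7-day recall windows are weeks 12-13, 25-26, 38-39 and 51-52. No session falls in any of them.
- C.15 lets a data collection call move two weeks either way. The month 3 window could then catch the week 11 or the week 14 session, but not both. The month 6 window could catch the week 27 session. That is at most one per window and two of ten in all, with none near months 9 and 12.

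The second limit matters more. Only workplace productivity enters the ratio. C.15 lets caregivers book sessions in the evening and at weekends, and C.14.2 expects a large share of participants, possibly most, to be past 65. A session outside paid work, or attended by someone without paid work, goes uncounted whatever the recall window.

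**2. How large is the uncounted item?**

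Inputs:

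- Sessions: 10 (opening summary).
- Length: 1 hour, **assumed**. C.2 says of the pilot, "Each session lasted approximately 1 hour". That pilot had four caregivers and 8 sessions each. The trial states no length.
- Value of time: $15-35 per hour, **assumed**.
- QALY gain: 0.01, 0.02 or 0.04, **assumed**.

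Time per ViCCY caregiver = 10 × 1 h = 10 h, or 125 × 10 = 1,250 h for the arm.

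Cost per ViCCY caregiver = 10 h × $15 to 10 h × $35 = $150 to $350.

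Change in ICER = cost ÷ QALY gain:

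| Assumed QALY gain | At $150 | At $350 |
|---|---|---|
| 0.01 | $15,000 | $35,000 |
| 0.02 | $7,500 | $17,500 |
| 0.04 | $3,750 | $8,750 |

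Homework is a sensitivity item only. Ten sessions leave nine intervals. At an assumed 0.5 to 2 h per interval this is 9 × 0.5 = 4.5 h to 9 × 2 = 18 h more, for totals of 14.5 to 28 h. The plan states no homework hours, and no number of boosters.

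**The case against.** Several counter-arguments have force.

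- **The list may be meant to cover it.** C.14.2 lists "number and length of intervention contacts" separately from nurse time and does not say whose time is priced. It also promises broad micro-costing and adherence to published panel standards; whether those call for participant time cannot be settled from the documents. The costing text as available has a sentence that breaks off, so an argument from absence needs care. This stands in part. One cannot say that the plan deliberately costs the provider's side alone, only that it never names caregiver time.
- **Productivity is a net difference.** A reader might infer that the ratio counts caregiver time only when ViCCY saves it, and that the ICER is therefore bound to favour ViCCY. The documents do not support that. The offset is "and the difference in workplace productivity collected for both study groups", so it can go against ViCCY, and paid work lost to a session inside a recall week could be captured. This stands: the omitted item has a known sign, but the whole ICER does not.
- **Time on the Health Information material also counts.** C.5 encourages both arms to spend half an hour a week for six months, about 26 × 0.5 = 13 h, which is more than the assumed session time. The encouragement is equal and cancels, but actual use may differ. This stands, and website use is tracked, so it can be checked.
- **Valuation is contestable.** Evening hours and the hours of retired people need not carry a wage, and homework may be the very self-care that the trial seeks. This stands, and is why the hourly value should be varied and homework kept to sensitivity analysis.
- **A payer perspective makes caregiver time irrelevant.** This does not rescue the plan, because the same perspective removes the productivity offset.
- **Bounds on cost and ICER are already planned.** C.14.2 does plan them, and caregiver time could be placed there, but it is not named.

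**Conclusion.** The inconsistency is real and confined to Aim 2. The numerator combines payer pricing of health care with one caregiver-side item, productivity, and names no charge for the caregiver-side item that coaching itself uses. For any positive value of time, a cost that only ViCCY incurs is left out.

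The size is illustrative: $150-350 per ViCCY caregiver, equivalent to $3,750-35,000 per QALY across assumed gains of 0.04 to 0.01. It rests on the pilot's session length and on an hourly value and QALY gains that the documents do not supply. A further claim, that the reported ICER will be too low overall, does not follow: productivity may move either way and actual use of the Health Information material may differ by arm. The primary efficacy analysis is untouched.

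**What to change.** In C.14.2, report two internally consistent ratios.

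1. **Payer ratio:** intervention and health care costs, with neither productivity nor caregiver time.
2. **Broader ratio:** the same costs, plus the productivity difference, plus caregiver time in coaching contacts (sessions, boosters and check-ins). Take the hours from the contact lengths already tracked, and leave out contacts already captured as absence from paid work.

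Vary the hourly value of caregiver time in sensitivity analysis. Treat homework time, and any between-arm difference in use of the Health Information material, as sensitivity ranges only. State in the text whose time the contact-length item prices.

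Contact lengths and website use are already to be recorded, so the work is one more analysis line and a rule against double counting. The downside is probably a less favourable broader ICER.

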
#### SPECIFIC AIMS

Informal caregivers have been called the "hidden victim" of illness.¹ Caregiving is demanding and stressful for those who provide extraordinary, uncompensated care for loved ones, often daily for months and years.² This stress may exceed the caregiver's ability to adapt,³ and many eventually become care recipients themselves as years of stress and deferred self-care put them at increased risk for illness.⁴-8 Self-care refers to those behaviors a person undertakes to maintain health and manage illness.⁴ Engaging in self-care may improve an individual's health status,¹⁰ defined as physical functioning and mental well-being.

Caregivers of adults with heart failure (HF) are an understudied group. HF is extremely common (12% of US adults after age 65). Most HF patients remain in the community through the end of their lives, depending on informal caregivers to assist them. The trajectory of illness in HF is highly variable, which limits the use of palliative care and respite services. As a consequence, caregivers of patients with HF (HF caregivers) report significant stress and poor self-care,  and there is a critical need to identify ways to improve self-care in HF caregivers. Without doing so, we risk losing these burdened caregivers to their own health issues.

Support interventions can encourage self-care by helping caregivers to focus on values, solve problems, and transform their goals into action.  We and others have shown that health coaching can improve self-care and outcomes in patients,  but studies of caregivers are limited, as are studies of the cost-effectiveness of support interventions for caregivers.  Even less is known about the effect of caregiver support on patient outcomes, although caregiver burden and stress have been shown to be associated with higher rates of hospitalization for patients with HF.  Although caregiving duties often confine caregivers to the home and many are unable to attend in-person sessions,  support interventions can be delivered by telephone  and the Internet.  Leveraging the growing availability and declining costs of – along with increasing receptivity of older adults to – technology,  we have developed and pilot tested a virtual support intervention (ViCCY ["Vicky"] – Virtual Caregiver Coach for You), that we propose to evaluate in HF caregivers.

Using a randomized controlled trial (RCT) design, we will enroll informal HF caregivers with poor self-care (Health Self-Care Neglect scale score ≥2), randomizing them 1:1 to an intervention or control group. Both groups will receive standard care augmented with Health Information (HI) delivered through the Internet, but the ViCCY caregiver group will also receive 10 front-loaded coaching support sessions tailored to individual issues. The control group will have access to the same HI resources over the same interval, using the same Internet program, but without coaching support. At baseline and 3, 6, 9, and 12 months, we will collect self-reported data on self-care, stress, coping, and health status. At 6 months, we will compare the efficacy of ViCCY (HI plus coaching) to HI alone to assess intervention efficacy using intent-to-treat analysis. Our pilot data suggest that addition of support provided by the health coach will make ViCCY more efficacious than HI alone. A sample of 250 caregivers (125/arm) will provide >90% power to detect significant differences between the groups on the primary outcome of self-care (Aim 1). We will collect quality adjusted life years (QALYs) and health care resource use in caregivers over 12 months to assess cost-effectiveness of ViCCY (Aim 2). To explore the effect of caregiver outcomes on HF patients' outcomes over a 12-month period (Aim 3) and knowing that not all HF patients will participate, we will consent a subgroup of the HF patients cared for by these caregivers (at least 40 dyads). We have the following Specific Aims:

- Aim 1: To compare the efficacy of ViCCY vs. HI alone in improving self-care. We hypothesize that, at 6 months after enrollment, caregivers randomized to ViCCY vs. HI alone will have **H1a**: Improved self-care measured with the Health Self-Care Neglect scale (*primary outcome*); **H1b**: Less self-reported stress measured with the Perceived Stress Scale (*secondary outcome*); **H1c**: Better coping measured with the Ways of Coping Questionnaire, short form(*secondary outcome*); and **H1d**: Better perceived mental and physical health status measured with the SF-36(*secondary outcome*).
- Aim 2: To estimate the cost and cost-effectiveness of ViCCY. We hypothesize that, at 12 months after enrollment, caregivers randomized to ViCCY vs. HI alone will have **H2a**: Higher QALYs measured with the SF-6D (short form six-dimension) derived from the SF-36 (secondary outcome); and **H2b**: Lower health care resource use (secondary outcome).
- Aim 3 (Exploratory): To explore the effect of caregiver outcomes on HF patient outcomes. We hypothesize that, at 12 months after enrollment, HF patients whose caregivers improve vs. not improve in self-care regardless of group will have **H3a**: Lower hospitalization rates; **H3b**: Fewer hospital days; **H3c**: Lower mortality rates; and **H3d**: Higher QALYs measured with the SF-6D.

If shown to be efficacious and cost-effective, our virtual health coaching intervention can easily scaled to support millions of caregivers worldwide. This application addresses the NINR strategic plan and is directly responsive to PA-18-150.

# RESEARCH STRATEGY A. SIGNIFICANCE

**A.1. Informal caregivers are stressed and their self-care is poor.** Informal caregivers carry the bulk of the responsibility for the care of ill, disabled, and elderly individuals. More than 42 million unpaid informal caregivers provide care to someone needing help because of a limitation in physical, mental, or cognitive functioning. As a group, informal caregivers have more stress, worse self-care, poorer health status, and higher mortality than non-caregivers. Caregivers often feel left alone to cope with problems, which exacerbates their stress. When stressed, caregivers are less vigilant and less motivated to engage in behaviors that will benefit themselves and their charges. In a study of 121 mainly female caregivers (mean age 61±13.4 years) of older family members, healthy self-care behaviors were lowest in those with high stress scores. In another study, after four years of follow-up, stressed caregivers were at 63% higher risk for mortality than non-caregiving controls. Together these studies illustrate the risk that informal care providers face when they defer self-care in response to the stress of caregiving.

A.2. Informal caregivers of patients with heart failure (HF caregivers) are an understudied population. Although informal HF caregivers face many of the same issues as other caregivers, they also face unique challenges. HF caregivers are older than other caregivers (mean 55.7 vs 49.4 years; p < 0.001).60 Both the patients and their caregivers often have multiple comorbid illnesses, making caregiving complicated. The trajectory of HF is highly variable with a gradual decline in function, so the need for caregiving lasts longer than for other populations. 61 Because of this unpredictability, neither palliative care to HF patients nor respite services to their caregivers are routinely offered. 13,20,60,62,63 HF is associated with poor physical capacity, depression, behavior problems, and cognitive impairment. Caregivers report difficulty coping with these patient-symptoms, 68 with the most stressful daily duties being providing emotional support, structuring and planning activities, and managing patient behavior and mood. 69-71 Caregivers must supervise and monitor complex care regimens and coordinate frequent hospitalizations, 72,73 the latter being so stressful that wellbeing is lower in caregivers than in patients when HF patients are hospitalized. HF caregiving is expensive, incurring lost-wages and out-of-pocket expenses; in a study of end-stage HF patients, 23% of families had lost all or most of their savings by the time the patient died. 75 These issues have a profound effect on caregivers' lives. 76,77 While caregivers of other populations often report satisfaction from caregiving, we see no evidence of caregiving satisfaction in HF caregivers. They are burdened, stressed, and poor in self-care. 30,69,71,78

A.3. Effective interventions are needed for HF caregivers. Few randomized controlled trials (RCTs) of interventions for HF caregivers have been published, 79 and of those, most have focused on improving HF caregiver burden, stress, or health status – not *caregiver self-care*. 76,80,81 The most common interventions involved psychoeducation facilitated by a registered nurse (RN), supplemented with face-to-face follow-up sessions, home visits, telephone calls and/or virtual monitoring. Two studies focused on helping caregivers support patient self-care, 81,83 but none focused on improving caregiver self-care. Few interventions reported a significant effect on one or more primary outcomes, and many were resource-intensive. For example, in a successful study in the Veterans Affairs system, 84 team-managed, home-based primary care with a dedicated care manager, 24-hour contact for patients, prior approval of hospital readmissions, and team participation in discharge planning effectively reduced caregiver stress and improved health status, but patient care costs increased by 12% at 12 months due to increased staffing. In an unsuccessful approach, a trial of a 12-week chair exercise program for HF patients hypothesized to decrease stress in caregivers demonstrated increased caregiver stress after six months, perhaps due to increased caregiving demands. We believe that few interventions have been effective because of failure to include elements argued to be essential in caregiving interventions: 1) a psychosocial rather than purely educational approach; 2) flexibility; 3) multidimensionality; and 4) sufficient intervention dose. We developed ViCCY to address these elements.

**A.4.** Internet-based virtual approaches can be used to support homebound caregivers. Successful implementation of potentially effective interventions is impeded when caregivers are homebound with caregiving duties. 30,87 Yet, such isolated individuals may be among the most stressed caregivers in need of support. 88,89 The home environment may be the best place to deliver an intervention, where distractions are predictable and privacy can be optimized. Home interventions are perceived as convenient, requiring less time commitment, travel costs, and waiting times; duration and timing of sessions can be flexible and accommodate caregiver preferences. Support is important to the success of psychosocial interventions, and virtual visual contact overcomes the challenges of lack of visual cues found in telephone-based interventions. A 2015 review of virtual interventions to support family caregivers concluded that caregivers were satisfied and comfortable with virtual support. Another review of eight open-label trials and 16 RCTs concluded that

Internet-based interventions were effective in reducing caregiver stress and improving their well-being. 

According to the 2015 US Census, 77% of the US population has broadband Internet access at home. 

Thus, live video-streaming is now possible for most people in the US at very low cost, making virtual support a potentially efficacious way to intervene with homebound caregivers. 

The population has broadband Internet access at home. 

Thus, a population has broadband Internet access at home. 

Thus, a population has broadband Internet access at home. 

Thus, a population has broadband Internet access at home. 

Thus, a population has broadband Internet access at home. 

Thus, a population has broadband Internet access at home. 

Thus, a population has broadband Internet access at home. 

Thus, a population has broadband Internet access at home. 

Thus, a population has broadband Internet access at home. 

Thus, a population has broadband Internet access at home. 

Thus, a population has broadband Internet access at home. 

Thus, a population has broadband Internet access at home. 

Thus, a population has broadband Internet access at home. 

The population has broadband Internet access at home. 

Thus, a population has broadband Internet access at home. 

The population has broadband Internet

**A.5.** Little is known about the cost-effectiveness of interventions for caregivers. Few cost-effectiveness analyses of support interventions have been performed in any chronically ill population. One review suggested that psychological therapies and psychosocial interventions were potentially cost-effective in people with dementia and their family caregivers.  In a pragmatic RCT providing an 8-session coping intervention to family caregivers of people with dementia, the cost-effectiveness acceptability curve  indicated >99% chance of being cost-effective in the short and longer term.  There is also evidence that psychological therapies provided by Internet are cost-effective.  No economic analyses of support interventions have been conducted in the HF population, but the annual cost associated with informal caregiving of patients with HF in the US was estimated at \$3 billion in 2010.  A Cochrane review examined the cost-effectiveness of home palliative care for adults with advanced illness, including HF, and their family caregivers,  but found inconclusive evidence and recommended more study. 

**A.6. Dyadic processes influence outcomes.** By definition, the caregiving relationship involves two people. Several studies, including our own, have demonstrated that dyadic processes influence outcomes in both HF patients and their caregivers. Several studies are descriptive, and no one has tested the influence of an intervention for caregivers on HF patient outcomes. The mechanism by which dyadic processes influence outcomes appears to be related to the quality of the relationship. Self-total Relationship quality influences burden, self-care behaviors, self-care behaviors, self-care behaviors, self-care behaviors, self-total decision-making, self-total decision-ma

**A.7. Theoretical Framework.** The proposed study is based on the Transactional Model of Stress and Coping (**Figure 1**). Stressful experiences such as caregiving demand – circumstances that give rise to real or perceived stress – are construed as person-environment transactions. Primary appraisal of demand involves assessment of its significance, which results in perceived burden. Secondary appraisal involves assessment of the resources available to cope with it. These appraisals lead to the coping effort. Without successful coping,

self-care is poor, which decreases health status in caregivers. Our virtual support intervention [ViCCY ("Vicky") -Virtual Caregiver Coach for You] addresses both appraisal and coping. Because stress does not affect all people equally, the intervention is tailored to individual appraisals and the factors most likely to influence demand and perceived burden. 122 A key strength of the Transactional Model of Stress and Coping is its recognition that both individual and environmental variables

[figure not shown]

Figure 1. Transactional Model of Stress and Coping. Caregiving demand is a stressor that initiates a process of primary appraisal (e.g., perceived burden) and secondary appraisal (e.g. controllability) in caregivers. These appraisals lead to coping efforts, which are supported with our ViCCY intervention. ViCCY is anticipated to promote caregiver coping and improve self-care (e.g., eat better, sleep more, exercise), which will improve caregiver health status. An intervention that improves caregiver outcomes may improve heart failure patient outcomes, but patient outcomes are not shown here. (viccy = virtual caregiver coach for you)

respond to coping. See Section C.5 and Table 3 for details on how the theory is used in ViCCY.

Scientific premise. This study builds on a body of evidence that is strong in describing stress in HF caregivers but weak in linking that stress to poor caregiver self-care. We have demonstrated in HF *patients* that self-care improves health status, 123,124 but the relationship between self-care and health status has rarely been tested in HF *caregivers*. 125 Health coaching has been shown to decrease perceived stress and improve

self-care and health status in other caregiver populations. Some of these studies have provided virtual support to homebound caregivers, and a few included older caregivers such as those we anticipate enrolling. However, very few studies have addressed the cost-effectiveness of interventions targeting informal caregivers. Furthermore, in addition to our primary aims, we will explore the impact of caregiver outcomes on HF patient outcomes. Although a growing body of research illustrates the influence of caregivers on patients and vice versa, (i.e., dyadic processes), very few intervention studies have explored the influence of the caregiver experience on patient outcomes.

